11.6.2 Retention in Care

- Offered to HIV positives who have successfully linked to HIV care (defined as date of first appointment at the HIV clinic (registering for care, and being assigned a patient number)).

The goal is that at least 85% of young HIV+ women linked to treatment will stay engaged in care. Using the Weltel model (Lester et al., 2010), ART adherence and treatment engagement SMS reminders combined with health status surveys will be sent every 3 months, aligned to school holidays for those in school, when the participants have access to phones. We will get informed consent to look at records in the CCCs to confirm self-report of clinic attendance, though one of the primary outcomes is study collected viral load as a measure of adherence.

HIV NEGATIVE COHORT

A subset of participants who test negative, consent and are eligible will be enrolled in the HIV negative cohort. They will be given a low-cost cell phone.

HIV Negative Cohort Eligibility Requirements:

Inclusion Criteria:

- Meets general eligibility criteria.
- Registered with the GIRLS study and assigned a valid Study ID number.
- Previously signed IC or if younger than 18 years of age (and not an emancipated minor) has a parent or guardian who provided consent in addition to their individual assent.
- Resides in the catchment area.
- HIV negative
- Determined to be “high risk” for HIV, based on key responses to key questions in the baseline CAPI survey (sexually active AND meet at least one or more of the following: Sexual partner is HIV positive or of unknown HIV status, reports three or more sexual partners in the last month, or reports her sexual partner has multiple sexual partners)
- Willing to receive SMS texts to assess HIV risk behaviors, condom use and HIV retesting behaviors and intentions.

We will collect locator information (telephone contacts) from N≈185 randomly-selected youth who test HIV-negative and identified as “high risk”, to participate in a primary prevention messaging intervention to support HIV risk reduction and adherence to HIV re-testing recommendations. They will receive an SMS text at 6 and 12 months with a health promotion message and will also collect HIV risk behaviors, condom use, and assess their HIV retesting behaviors and intentions. At 12 months, we will re-test them for HIV and they will also complete a face-to-face (or telephone) interview on barriers and facilitators to accessing HIV prevention services. If a phone interview is

conducted, participant's identity will be confirmed by asking the participant to provide three names used at enrollment as well as their current age, so that her identity may be ascertained correctly. **Those not enrolled into the cohort will be referred for prevention and other services** (partner and family testing, PrEP, other family planning (contraception) methods, STI screening and treatment, drug use counseling, mental health services, social and nutritional support, legal services, sexual and gender based violence services and others that might be identified during the interview/risk assessment with participants).

Follow Up SMS Surveys

Participants will be educated on how to complete surveys on their phone at the time of enrollment. At this time, their cell phone number will be linked to their study ID. Each participant will be assigned a unique password/PIN code and a memory word. When they are sent the survey, they will need to enter their password to participate. If the participant forgets their password, they will be required to enter their memory word and if this fails, they will be required to visit the study site in person for identity verification and allocation of a new pass word. Once study staff ensures that the phone user is the study subject, (receiving texts is free in Kenya) staff will then wirelessly transfer airtime, so the cohort participant can send surveys using short message service (SMS) texting (Kumar, Chen, Paik, & Subramanian, 2009). In this way we will ensure follow up with the cohort regardless of where they live (if they moved since baseline). The SMS surveys will collect the following types of information, including but not limited to:

- HIV testing option and test experience
- Successful linkage
- Sexual risk behaviors
- Retention in care
- Adherence barriers and facilitators
- Willingness to re-test (for subset of HIV negatives)
- Status disclosure

[figure not shown]

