Primary Endpoint(s)	
Primary outcomes of interest for Aim 1 are based on the HIV prevention and treatment continua as outlined below:
 
 • Recruitment/Seek: Ability to identify and recruit female youth that are high risk for HIV infection using two seek strategies (home-based vs. community-based) 
 ○ The proportion of youth in the community who accept study screening (estimated from total youth approached as the denominator); ○ The proportion of youth who accept study enrollment (estimated from youth screened and eligible as the denominator); • Testing: 
 ○ Testing uptake by different testing modalities; ○ Completion of confirmatory testing; ○ Proportion that are positive; ○ Among those who are positive, completion of baseline collection of CD4 and viral load tests. 
Outcomes of interest for Aim 3 economic evaluation to determine the comparative cost effectiveness of the seek, test, link, and prevention interventions are:
 
 • Compute the cost per HIV-infected female youth identified under each 'seek' strategy (home-based vs. community based); • Compute the cost per HIV-infected female youth identified under each 'test' strategy (self-testing, staff delivered HTS testing, standard facility-based HTS); • Calculate the incremental cost-effectiveness ratio of the adaptive linkage to care intervention among HIV positive female youth; • Compute the cost of the SMS prevention intervention among HIV negative female youth.
Secondary Endpoint(s)	
Secondary outcomes of interest for Aim 2 are based on the HIV prevention and treatment continua as outlined below:
 
 • Linkage to Care: 
 ○ Percent of females who tested positive that attended a first HIV care appointment at an HIV Comprehensive Care Center (CCC) ○ Time to link to care after positive confirmatory test result. • Retention in Care: 
 ○ Completion of viral load testing at 12 months; ○ Reported appointment attendance via SMS and verification by study staff at 3, 6, 9, and 12 months. • Primary Prevention (N≈185): 
 ○ Proportion reporting HIV risk behaviors, and condom use, at 6 and 12 months; ○ Proportion who re-tested at 12 months; ○ Proportion who tested positive at 12 months.

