11.8 Assessment of Participant Compliance with Study Intervention(s)

Compliance with study interventions and recommendations will be assessed in the longitudinal cohorts.

HIV positive Cohort:

[figure not shown]
- We will be working with Homa Bay County, Ndhiwa and Mbita health facilities. Participants identified as HIV+ will be referred to Government of Kenya HIV Care centers referred to as Comprehensive Care Centers (CCC) via the intervention described for ART initiation for those who meet treatment criteria (See Figure 8, Adaptive Intervention).
- We will have a database of all participants who tested positive so when a participant goes to the referral clinics (comprehensive care centers (CCCs)) she will be identified using the tracking card. After a girl has received a positive test result she will be given a card with the contact information of our study staff (or other contact to be determined) at the clinic. We will then check with the clinics to see if that participant has visited.
- Among those that have successfully linked to care, adherence to antiretroviral medication and clinic visits will be assessed by self-report via an SMS text survey at 3, 6, 9 and 12 months of follow-up, and a repeat of viral load measure at 12 months. We will also review her medical records at the CCC to confirm her self-report of clinic attendance.
- All HIV positive girls will complete an exit interview at month 12 of follow up that will identify barriers and facilitators to seeking HIV care services after receiving a positive diagnosis. This exit interview will also capture information about the use of economic incentive for linkage.

HIV negative Cohort:

- Response rate to SMS survey at 6 and 12 months to collect HIV risk behaviors, condom use and willingness to retest for HIV among the approximately 185 HIV negative high risk girls on follow up.
- At 12 months, whether or not we were able to re-test the participant for HIV at a site of their choice.
- At 12 months, completion of face-to-face (or telephone) exit interview on barriers and facilitators to accessing HIV prevention services. If a phone interview is conducted, participant's identity will be confirmed by asking the participant to provide three names used at enrollment as well as their current age, so that her identity may be ascertained correctly.

We have included a flow chart below that brings all the interventions together, Figure 10.

Figure 10. A flow chart of study activities

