Linkage to Care: Percent of females who tested positive that attended a first HIV care appointment at a CCC; time to link to care after positive confirmatory result.	GIRLS study project database, medical record review at CCC, exit interviews.	2 weeks after first randomization; 1 week to re-randomize; 2 weeks after second randomization (5 weeks total from start of linkage pilot). Exit interview collected at 12 months.	Descriptive statistics; survival plots for occurrence and timing of linkage. Cox proportional hazards model for differences in likelihood and timing of linkage between the two treatment conditions; median time to linkage. Predictors of successful linkage to care.	N≈108
Retention in Care: Completion of viral load testing one year after positive confirmatory test; self-report of appointment attendance. Review of medical records to confirm self-report of clinic attendance.	SMS surveys, medical record review, exit interviews.	3, 6, 9, 12 months for SMS surveys. Medical record review to confirm clinic attendance self-report. Exit interview collected at 12 months.	Frequencies; assess number retained in care at 12 months. Proportion who complete viral load testing at 12 months.	N≈108
Primary Prevention: HIV risk behaviors, condom use, and HIV re-testing of a sub-sample of high risk HIV negatives	SMS surveys GIRLS study project database	6 and 12 months for SMS surveys. At 12 months, exit interview and re-testing	Descriptive statistics; new HIV diagnosis at 12 months.	N≈185
Aim 3 economic evaluation	Measures (Sources)	Data Collection Timeline	Data Analysis	
Economic evaluation to determine the comparative cost effectiveness of the seek, test, link, and prevention interventions.	GIRLS study project database	Accrual and follow-up period.	Micro-costing of the cost per HIV infected person under each seek and test strategy; incremental cost effectiveness of linkage to care intervention for HIV +; cost analysis of SMS intervention and re-testing for HIV negative females.	

15.10 Appropriate Methods and Timing for Analyzing Outcome Measures.

See Table 1: Evaluation Plan.

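### The appointment-attendance endpoint rests on SMS self-report, with clinic records only confirming it, so a linked girl who does not reply has no defined attendance value

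*Combined protocol and SAP*

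**What the plan says.** Section 6 and Section 13.2 list two retention endpoints. The first is "Completion of viral load testing at 12 months". The second is "Reported appointment attendance via SMS and verification by study staff at 3, 6, 9, and 12 months".

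Section 11.8 states how the second is measured among girls who have linked: "adherence to antiretroviral medication and clinic visits will be assessed by self-report via an SMS text survey at 3, 6, 9 and 12 months". It then gives the record review its purpose: "We will also review her medical records at the CCC to confirm her self-report of clinic attendance". Section 11.6.2 says the same ("We will get informed consent to look at records in the CCCs to confirm self-report of clinic attendance"), as does the retention row of Table 1 ("Review of medical records to confirm self-report of clinic attendance"). The logic model in Appendix B repeats it. Table 1 names the sources as "SMS surveys, medical record review, exit interviews" and plans frequencies and a count of those retained at 12 months.

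Section 11.6.2 sets a goal that at least 85% of those linked stay engaged in care. No section says how a girl who does not answer a survey is classified, or which source prevails if the SMS and the record disagree.

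**The concern.** Every statement of what the retention record review is for presupposes a self-report to be confirmed. Followed literally, a linked girl who sends no reply has nothing to confirm, and her attendance at that time point is undefined.

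Silence may well be related to the outcome. Replying needs access to a phone and a password. If the password and then the memory word fail, participants are told "they will be required to visit the study site in person for identity verification and allocation of a new pass word". Surveys are timed to school holidays because that is when schoolgirls have phones. A girl who disengages could stop replying and stop attending together. This link is an inference, but a plausible one.

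A second source is within reach. Section 11.6.1 defines linkage by registration at the HIV clinic and assignment of a patient number, so a clinic file should have been opened for each linked girl, and consent to view such files is planned. What is at stake is whether the reported attendance figure describes linked girls or only those who kept answering.

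**Working it through.** **Cohort size.** Expected yield 9% of 1,200 (Sections 10.2 and 15.11): 0.09 × 1,200 = 108, which reproduces the N≈108 in Table 1. The documents give no precision, power or response-rate figure for retention.

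**Linked girls, from the planning figures in Section 15.11.** About 20% of 108 link after the first step, and at least 60% of the remaining 86 link later: 0.2 × 108 + 0.6 × 86 = 21.6 + 51.6 ≈ 73.

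**Assumptions, not in the documents.** Let r be the SMS response at a time point (60% or 80%), p the proportion in care among responders (90%), and q the proportion in care among non-responders (60% or 80%). Silent girls number (1 − r) × 73, which is about 29 at r = 60% and 15 at r = 80%.

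**Formulas.** Responders only = p. Silence counted as out of care = r × p. All linked girls = r × p + (1 − r) × q. Ceiling, with all silent girls in care = r × p + (1 − r).

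| r | Responders only | Silence = out | All girls, q = 60% | All girls, q = 80% | Ceiling |
|---|---|---|---|---|---|
| 60% | 90% | 54% | 54 + 24 = 78% | 54 + 32 = 86% | 94% |
| 80% | 90% | 72% | 72 + 12 = 84% | 72 + 16 = 88% | 92% |

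**Break-even for 85%.** Solve r × p + (1 − r) × q = 0.85. At r = 60%, q = (0.85 − 0.54)/0.4 = 77.5%. At r = 80%, q = (0.85 − 0.72)/0.2 = 65%. Below these values responders alone sit above the goal while the full group does not. Above them both meet it, yet counting silence as out of care still falls short.

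**Higher response.** At r = 90% the spread narrows but does not vanish: silence as out gives 81%, and all girls with q = 60% gives 81 + 6 = 87%.

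**Denominator.** Table 1 gives N≈108 for retention. Sections 11.6.2 and 18.2.1 restrict retention and its surveys to girls who linked, while Section 11.6.1 sends surveys to all HIV-positive girls enrolled for follow-up. If only 73 link, retention over 108 cannot exceed 73/108 = 68%, so the 85% goal makes sense only among linked girls.

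**The case against.** Four points on the other side carry weight.

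- **Retention as a whole does not rest on SMS.** A reader might infer that it does. Viral load completion is listed first, is collected by study staff and is independent of SMS, and an exit interview is also planned. This stands, and limits the point to attendance. Viral load completion does not fill the gap, however: it is a single 12-month measurement, it needs a visit to a study site, and it says nothing about months 3, 6 and 9.
- **The plan does not exclude non-responders' files.** A reader might infer a written rule that leaves them without a value. There is none. The endpoint includes verification by staff, Table 1 lists record review as a source in its own right, and Section 11.8 has staff check with clinics whether a girl has visited, although that check concerns linkage. Universal review is a possible reading, but the same Table 1 row limits the review to confirming self-report. Undefined is the accurate word.
- **The CCC record is not an unbiased standard.** The documents name three partner sites and do not say whether files elsewhere will be reached. A girl who transfers could look lost locally while her SMS reply shows her in care. This stands, and the remedy must allow for it.
- **Non-response is mitigated.** Phones are supplied, airtime is transferred by staff, KSh 100 is paid per survey, and Section 12.1.3 allows calls and tracing. These measures should reduce silence but do not say how to classify what remains.

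**Conclusion.** The point holds for appointment attendance, one of two secondary retention endpoints. SMS self-report is the stated measure, the record only confirms it, and a linked girl who does not reply has no defined value.

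The calculation shows that a bias is possible; it does not estimate one. With 60–80% response and 90% of responders in care, the reported figure could be 90% or 54–72% according to how silence is treated. The figure over all linked girls would be 78–84% or 86–88% according to whether 60% or 80% of non-responders are in care. All these rates are assumptions.

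A reader might infer that the study could falsely claim success on retention. The documents do not support that: 85% is a descriptive goal with no test, success criterion or stopping rule, and the planned analysis is frequencies within a secondary-objective pilot. The consequence is a figure whose reading against that goal may depend on an unwritten choice. It is worth settling before follow-up data accrue, since the second source is already to be opened.

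**What to change.** In Sections 6, 11.6.2, 11.8 and 13.2 and in Table 1:

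1. State that CCC records are reviewed for every linked girl at 3, 6, 9 and 12 months, whether or not she replied, and make the record the main attendance measure.
2. Where no local record of attendance is found, use the SMS report, exit interview or tracing to identify transfers. Report transfers and files that cannot be located as separate categories, and say how each counts towards the 85% goal.
3. Report the SMS response rate, and agreement between SMS and record, as secondary results.
4. Use linked girls as the denominator for the 85% goal, and reconcile N≈108 in Table 1 with Sections 11.6.1, 11.6.2 and 18.2.1. Carry the wording into Appendix B.

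The cost is wording plus the files of non-responders: about 15–29 per time point on the figures above, within a cohort of about 108. The remaining weakness is that attendance at non-study clinics may be under-captured, which is why transfers should be shown separately.

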11.6.3 Final Study Visit (for HIV+ and HIV- Cohorts)

The HIV+ cohort enrollees will be asked to come to the study site (Homa Bay County Referral Hospital, Mbita Health Centre, or Ndhiwa Health Centre) to get a repeat viral load specimen collection done. In fulfillment of Aim 2b, which is to identify barriers and facilitators (social demographic, clinical, health system related) to seeking HIV care services after receiving a positive diagnosis, all HIV positive cohort participants will be invited to an exit interview administered by study staff on computer tablets at the study sites. The purpose of the interview is to capture barriers and facilitators to HIV care and treatment services. These data will provide more contextual understanding of care seeking (i.e., different questions being assessed than by SMS) for young HIV+ women. We will interview all participants in the HIV positive cohort so that we are able to capture different linkage, retention, and ART adherence experiences.

The HIV- cohort enrollees will be contacted to arrange for HIV re-testing. At this time, the HIV- cohort participants will be invited to an exit interview administered by study staff on computer tablets. The purpose of the interview is to capture barriers and facilitators to HIV prevention services. The data will be informative for understanding HIV prevention strategies.

The figure below summarizes GIRLS study follow-up timeline and outcome measures after successful linkage to care.

Figure 9: Follow-up and outcome measures after linkage to care

11.7 Study supplies, distribution, and accountability

11.7.1 Study supplies storage.

- HIV Testing Services:** HIV test kits based on GoK HIV testing algorithm (currently Determine HIV 1/2 for screening, First Response™ HIV Care 1-2.0 for Confirmatory and Unigold™ for the Tie Breaker; OraQuick ADVANCE® Rapid HIV-1/2 Antibody Test for oral fluid HIV self-testing), will be stored between 2 – 27°C, in a dry location, away from direct sunlight and avoiding extremes of hot or cold conditions (as per manufacturer's instructions provided in the kit insert) at study office and in the mobile health secured supply-chest. Kit components are stable until expiration date when stored as directed. We

will collect data on storage conditions (e.g., temperature tracking log), duration of storage, date self-test kit dispensed etc. We will also request that the meteorological department in Homa Bay provide data on average temperatures in the study locations during the study period. This information will not be used for weather prediction but as a proxy for temperature monitoring log for the test kits issued to participants. Meteorological data is part of QA for the test kits and will not be shared with participants.

- **PIMA CD4 cartridge** will be stored at 2–30° temperature range (as per manufacturer's instructions provided in the kit insert).
- **Condoms:** Condoms will be stored at study office and in the mobile health secured supply-chest.

11.7.2 Study Accountability Procedures:

The designated study personnel supported by the field site coordinator will be responsible for tracking study test kits and supplies, and will be responsible for maintaining logs of study supplies/interventions administered to participants.

- **HIV Testing Services (HTS):** Documentation of test kits (including **PIMA CD4s**) administered will be kept in the inventory log by the field study coordinator and in a log by the research assistants/nurses who conduct HTS.
- **Condoms:** Documentation of condoms given will be kept in the inventory log by the field study coordinator/clinical officer and in a log by the research assistants/nurses who distribute condoms.

11.8 Assessment of Participant Compliance with Study Intervention(s)

Compliance with study interventions and recommendations will be assessed in the longitudinal cohorts.

HIV positive Cohort:

[figure not shown]
- We will be working with Homa Bay County, Ndhiwa and Mbita health facilities. Participants identified as HIV+ will be referred to Government of Kenya HIV Care centers referred to as Comprehensive Care Centers (CCC) via the intervention described for ART initiation for those who meet treatment criteria (See Figure 8, Adaptive Intervention).
- We will have a database of all participants who tested positive so when a participant goes to the referral clinics (comprehensive care centers (CCCs)) she will be identified using the tracking card. After a girl has received a positive test result she will be given a card with the contact information of our study staff (or other contact to be determined) at the clinic. We will then check with the clinics to see if that participant has visited.
- Among those that have successfully linked to care, adherence to antiretroviral medication and clinic visits will be assessed by self-report via an SMS text survey at 3, 6, 9 and 12 months of follow-up, and a repeat of viral load measure at 12 months. We will also review her medical records at the CCC to confirm her self-report of clinic attendance.
- All HIV positive girls will complete an exit interview at month 12 of follow up that will identify barriers and facilitators to seeking HIV care services after receiving a positive diagnosis. This exit interview will also capture information about the use of economic incentive for linkage.

HIV negative Cohort:

- Response rate to SMS survey at 6 and 12 months to collect HIV risk behaviors, condom use and willingness to retest for HIV among the approximately 185 HIV negative high risk girls on follow up.
- At 12 months, whether or not we were able to re-test the participant for HIV at a site of their choice.
- At 12 months, completion of face-to-face (or telephone) exit interview on barriers and facilitators to accessing HIV prevention services. If a phone interview is conducted, participant's identity will be confirmed by asking the participant to provide three names used at enrollment as well as their current age, so that her identity may be ascertained correctly.

We have included a flow chart below that brings all the interventions together, Figure 10.

Figure 10. A flow chart of study activities

